4.2 Exclusion Criteria

- Physically unable or unwilling to participate in recommended exercise programs or travel to UCSF on a monthly basis
- Presence of permanent pacemaker or implantable medical device.
 - Artificial joint prostheses and venous filters are allowed.

5. Study Drug

5.1 Lupron Depot (Leuprolide acetate for depot suspension) Description, Formulation and Storage

5.1.1 Description

Lupron Depot (Leuprolide acetate) is a synthetic nonapeptide analog of naturally occurring gonadotropin releasing hormone (GnRH or LH-RH).

5.1.2 Formulation

Lupron Depot (Leuprolide acetate) for injection is a sterile, aqueous solution intended for subcutaneous injection. It is available in a 2.8 mL multiple-dose vial containing leuprolide acetate (5 mg/mL), sodium chloride, USP (6.3 mg/mL) for tonicity adjustment, benzyl alcohol, NF as a preservative (9 mg/mL), and water for injection, USP. The pH may have been adjusted with sodium hydroxide, NF and/or acetic acid, NF. The pH range is 4.0 to 6.0.

The vial is packaged as a 4 Day Patient Administration Kit with 14 disposable syringes and 28 alcohol swabs, NDC 0185-7400-85.

5.1.3 Storage

Store below 77°F (25°C). Do not freeze. Protect from light; store vial in carton until use.

Guidelines for Administration: See Treatment and Dose Modification section of protocol

5.2 Eligard Description, Formulation, and Storage

5.2.1 Description

Eligard is a sterile polymeric matrix formulation of leuprolide acetate, a GnRH agonist.

5.2.2 Formulation

Eligard is prefilled and supplied in two separate, sterile syringes whose contents are mixed immediately prior to administration. The two syringes are joined and the single dose product is mixed until it is homogenous.

Eligard is administered subcutaneously, where it forms a solid drug delivery depot.

5.2.3 Storage

Store at 2 – 8 °C (35.6 – 46.4 °F)

Guidelines for Administration: See Treatment and Dose Modification section of protocol.

5.3 Zoladex Description, Formulation and Storage

5.3.1 Description

Zoladex (goserelin acetate) is a synthetic decapeptide analog of gonadotropin releasing hormone (GnRH or LHRH).

5.3.2 Formulation

Zoladex (goserelin acetate) depot is supplied as a cylindrical rod of biodegradable and biocompatible D-L Lactide-glycolide copolymer. Each ZOLADEX depot contains goserelin acetate equivalent to 3.6 mg of goserelin. This depot is presented in a sterile ready-to-use syringe with a 16 gauge needle for a single subcutaneous injection. This single-dose syringe is assembled with a protective sleeve (SafeSystem™) in a sealed, sterile pouch that contains a desiccant.

5.3.3 Storage

Protect from light and moisture. Store in the intact package between 2°C and 25°C.

Guidelines for Administration: See Treatment and Dose Modification section of protocol

5.4 Telstar Description, Formulation, and Storage

5.4.1 Description

5.4.1 Trelstar is a synthetic decapeptide agonist analogue of gonadatropin release hormone (GnRH).

5.4.2 Formulation

Trelstar is administered as a single intramuscular injection in either buttock. The lyophilized microgranules are to be reconstituted in sterile water. No other diluent should be used. Due to different release characteristics, the dosage strengths are not additive and must be selected based on the desired dosing schedule: 3.75 mg every 4 weeks, 11.25 every 12 weeks or 22.5 mg every 24 weeks.

5.4.3 Storage

Store at 20-25°C (68-77°F). [See USP Controlled Room Temperature.] Do not freeze Trelstar with MIXJECT.

Guidelines for Administration: See Treatment and Dose Modification section of protocol

6. Drug Treatment Plan

6.1 LHRH Route of Administration, Primary Side Effects, and Dose Modifications and Dosing Delays

6.1.1 Route of Administration

The LHRHa injections will be delivered either subcutaneously (Eligard®, Zoladex®) or intramuscularly (Lupron Depot® or Trelstar®) by a trained health care provider while on protocol therapy.

6.1.2 Primary Side Effects

Hot flashes, decreased libido, breast pain, gynecomastia, hyperglycemia, hypercholesterolemia, decreased bone mineral density, fatigue, anemia, mood changes.

6.1.3 Drug Supply

The drugs will be commercially supplied.

For a complete description of these drugs, please see the package inserts.

7. Study Activities

7.1 Study Schedule

	Pre-Study/ Screening (within 6 weeks of Day 1 of Study)	Day 1 Study Visit	End of Every Month (+/- 2 weeks)	End of Every 3 Months (+/- 2 weeks)	End of Month 12 Study Visit (+/- 2 weeks)	Follow Up Visit ¹ (6 months after completion of STAND clinic)
Physical Exam with Health Care Provider (Both study arms)	X	X		X	X	X
LHRH Analogue ^a		X		X		
Exercise, Nutrition, Symptom Management counseling ^b		X	X			
Educational Modules (STAND clinic arm only)		X	X			
Counseling, review tests and questionnaires				X	X	X
Informed Consent	X					
Randomization	X					
Demographics	X					
Past Medical History	X					
Concomitant Medications ⁱ	X	X		X	X	
QOL/empathy Questionnaires ^c		X		X	X	X
Co-morbidity Assessment ^d	X					
Ratio of 2 nd to 4 th digit finger length ^e	X					
Weight/Body Mass Index/Percent Body Fat ^f	X	X		X	X	X
ECOG Performance		X		X	X	

DXA Scan ^f	X				X	
HRpQCT (optional) ^h	X				X	
Serum PSA ⁱ	X	X		X	X	X
Serum testosterone		X ^j			X	X
Serum 25-(OH) vitamin D level		X		X	X	
Fasting glucose/lipid panel, HgbA1c, insulin level		X		X	X	X
Hemoglobin A1c		X		X	X	X
Plasma/serum for banking ^k		X		X	X	X
PBMCs for germline polymorphisms (optional) ^k		X				

a. Patients who have started ADT prior to study enrollment will be kept on same schedule for next dose of LHRH analog and provider visit while on study. On study patients will receive LHRH agonist every 3 months (+/- 1 week), on same day as health care provider visits whenever possible.

b. Patients randomized to the STAND clinic will visit with one of three specialties (exercise, nutrition, symptom management) at each monthly visit. The total number of visits with each specialty will be four on an every 3-month basis. The rotation of the schedule of providers may be adjusted depending upon availability of provider and patient. Patients randomized to the usual care study arm will be referred to nutrition, exercise, and symptom management services upon patient request or as deemed necessary by health care provider.

c. Quality of life questionnaires to be completed include SF-12, EPIC-26, Hot Flash Related Daily Interference Scale, Lee Fatigue Scale, PHQ-9, Attentional Functional Index, Exercise questionnaires, and empathy quotient-8 (see Appendix 2). These questionnaires may be completed online ahead of scheduled visit or at the time of clinic visit, either electronically or on paper. The PHQ-9 scale must be completed on paper on the same day as study visit, and reviewed and signed by health care provider prior to patient discharge from clinic.

d. Assessed with Charlson Comorbidity Index (see Appendix 3)

e. Measured by caliper (see Section 1). For patients already enrolled on study who did not complete at baseline, this measurement will be performed at the next planned study visit.

f. Percent body fat to be measured using bioimpedance device on C1D1, every 3 months, and end of month 12 on study (see Appendix 4)

g. Bone mineral density measured at the lumbar spine, total hip, and femoral neck (performed within 12 weeks of day 1 of study)

h. High resolution quantitative peripheral CT of the radius and tibia (optional)

i. Baseline PSA determined during screening if not already taking ADT

j. Include screening assessment or serum testosterone of prior receipt of ADT

k. See Appendix 6 for collection and processing instructions

l. Following completion of STAND clinic participation, patients will be followed by telephone visit after 2 and 4 months to assess adherence to recommended diet/exercise plans. At 6 months, patients will return for clinic assessment.

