7.2 Screening Visit (within 6 weeks of Day 1 of Study)

Screening procedures and informed consent as well as written health information authorization must be completed within 6 weeks of day 1 of study. All research-related procedures will be conducted after patient has signed written consent to participate in the study.

These procedures include:

- Physical exam and medical history
- Demographics and disease characteristics:
 - Date of prostate cancer diagnosis
 - Gleason grade and PSA at the time of diagnosis
 - Type and date of prior local therapy (if any)
 - Date of ADT initiation and indication (adjuvant, biochemical relapse, or metastatic disease)
 - Concurrent use of anti-androgen (yes/no)
 - Concurrent radiation therapy (yes/no)
 - Metastatic status at time of study entry (none, bone only, soft tissue, any visceral)

Clinical Assessment

- Co-morbidity assessment by Charlson Co-morbidity Scale (Appendix 3)
- Quality of life questionnaires (see Appendix 2):
 - SF-12, EPIC-26, HFRDIS, Lee Fatigue Scale, PHQ-9, Attentional Functional Index, exercise patterns, empathy scale
- Concomitant medication
- Weight and body mass index
- Assessment of ratio of 2nd digit to 4th digit finger length using caliper assessment

Radiographic Assessment

- DXA Bone Density Scan (completed within 12 weeks of Day 1 of study)
- High resolution peripheral quantitative CT scan of the distal tibia and radius (optional)

Laboratory Assessment

- Baseline PSA measurement
- Serum testosterone (if prior receipt of androgen deprivation therapy)

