7.3 Randomization

Once eligibility is confirmed and patient has signed informed consent, patients will be stratified according to duration of ADT prior to study entry (≤ 3 months vs. 3-6 months) and body mass index at study entry (≤ 30 vs. > 30). They will be randomized with equal probability to one of the two study arms from within each of the six strata. Balance in treatment assignment will be achieved using a randomized block design. Randomization will be carried out via computer generated random assignment. Randomization must be completed within 6 weeks of day 1 of study.

A non-randomized pilot cohort of patients receiving concurrent chemohormonal therapy will be enrolled in parallel to assess the feasibility of STAND clinic participation in this patient population.

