7.4 Day 1 Study Visit

7.4.1 Clinical Assessment

- Physical examination
- Concomitant medications
- ECOG Performance Status
- Height, weight, body mass index, and percent body fat by bioimpedance measurement (see Appendix 6)
- LHRH Analogue

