8.2 Patient-Reported Outcomes

At baseline and every 3 months patients will complete quality of life and other questionnaires as outlined in Appendix 2. Patients will complete the questionnaires online within one week of study visit or at the time of study visit, either electronically or on paper. The PHQ-9 questionnaire must be completed on paper during the study visit. It is mandatory that the responsible health care provider for the study visit review and sign the results of the PHQ-9 prior to patient discharge from clinic.

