9.8.1 Analytic Plan for the Primary Objective

Two-sample t-test will be used to compare the mean percent change from baseline in percentage body fat after 12 months of study participation. The changes in percentage body fat across the

different time points will be evaluated using repeated measures analysis of covariance. To further characterize the patterns over the time and investigate the effect of treatment arm assignment, a linear mixed model will be applied with adjusting for stratification factors and covariates including Charlson co-morbidity index score, age, and baseline depression score as measured by PHQ-9. Patients who do not have a baseline or end-of-month 12 percentage body fat measurement, or those that start medications known to affect body fat/body weight during the course of the 12-month study, including metformin, insulin, corticosteroids, mirtazapine, or megestrol, will be excluded from the primary endpoint analysis. In an exploratory analysis, these patients will be retained to assess the impact of STAND clinic participation on changes in percentage body fat over time both before and after initiation of medical management.

For the non-randomized chemohormonal cohort, the point estimate and 95% confidence interval of the percentage of completed STAND clinic visits will be reported.

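### Sections 7.1, 7.2 and 7.4 disagree on when the first questionnaires are completed, no section names the baseline form, and the 7.1 timing falls after randomisation

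*Combined protocol and SAP*

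**What the plan says.** **Schedule table (7.1).** The row "QOL/empathy Questionnaires ^c" has no mark in the screening column. Its first mark is at Day 1, followed by the 3-monthly, month 12 and follow-up visits. Randomisation is marked in the screening column. Day 1 also carries the first counselling contact and the first educational module for the STAND arm; 7.5 likewise covers Day 1 together with the monthly visits.

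**Screening visit (7.2).** The screening clinical assessment includes "SF-12, EPIC-26, HFRDIS, Lee Fatigue Scale, PHQ-9, Attentional Functional Index, exercise patterns, empathy scale". The window is: "Screening procedures and informed consent as well as written health information authorization must be completed within 6 weeks of day 1 of study".

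**Day 1 visit (7.4).** The clinical and laboratory lists include body fat by bioimpedance, fasting bloods and performance status, but no questionnaire.

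**Randomisation (7.3).** Only confirmed eligibility and signed consent must come first. On timing: "Randomization must be completed within 6 weeks of day 1 of study".

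**Patient-reported outcomes (8.2).** "At baseline and every 3 months patients will complete quality of life and other questionnaires as outlined in Appendix 2". The word baseline is not tied to a visit.

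**Analysis (9.7.2, 9.8.1, 9.8.2).** The questionnaire endpoints are changes from baseline to 12 months. The linear mixed model for body fat adjusts for "baseline depression score as measured by PHQ-9". Section 9 does not define baseline for any questionnaire. By contrast, footnote f to the 7.1 table fixes the first body-fat measurement at C1D1.

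**The concern.** The two candidate baselines are not interchangeable. A form completed on Day 1 is completed after allocation. Nothing in the documents masks that allocation, and a man asked to attend monthly STAND visits can hardly be unaware of it. A self-report taken then can reflect disappointment or reassurance about the arm. In the STAND arm, it can also reflect a counselling session or module delivered the same day, because no order is set between the form and the session.

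If the baseline differs between arms for these reasons, the difference passes into every change score. It also means that a mixed model described as adjusting for baseline depression would adjust for a value measured after randomisation. If staff follow different sections for different men, the men do not share a common baseline either.

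**Working it through.** The plan states no figure on this point, so the check is a comparison of sections followed by a sensitivity illustration.

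**1. Where the first form falls**

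| Source | Screening | Day 1 |
|---|---|---|
| 7.1 table | blank | marked |
| 7.2 list | full set | not applicable |
| 7.4 lists | not applicable | none |
| 8.2 | baseline, no visit named | baseline, no visit named |

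Following 7.1 gives only a Day 1 form before follow-up. Following 7.2 and 7.4 gives only a screening form. The blank screening cell does not look like a column lost in text extraction: the performance-status row has the same pattern (blank at screening, marked at Day 1) and agrees with 7.4.

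**2. Order relative to allocation**

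Randomisation is in the screening column, up to 6 weeks before Day 1, so a form completed at Day 1 follows it. Footnote c and 8.2 allow early online completion (within one week of the visit in 8.2), but both require the PHQ-9 on paper at the visit. Under 7.1, then, the PHQ-9 used as a covariate is a post-randomisation value.

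The recall periods in Appendix 2 do not remove the exposure. The Lee Fatigue Scale and the Attentional Functional Index ask about the present. The PHQ-9 covers two weeks and EPIC-26 four weeks, and both periods can lie wholly after an allocation made up to 6 weeks earlier.

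**3. Gap between the two candidates**

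- 12 months = 365.25 / 7 = 52.2 weeks from a Day 1 form.
- From a screening form: up to 52.2 + 6 = 58.2 weeks.
- The difference is up to 6 / 52.2 = 11.5% of the planned interval.

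**4. Illustration of size**

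From the documents: 32 evaluable men per arm (9.2). This is the body-fat target, borrowed here. Assumed, with no basis in the documents: equal SD at both times, correlation 0.5, and a one-arm baseline shift d of 0.1 to 0.3 SD that does not persist to month 12.

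- SD of change = SD × √(2 × (1 − 0.5)) = 1 SD.
- SE of the arm difference = √(2/32) = 0.25 SD.
- Movement of the arm difference in SE units = d / 0.25.
- Two-sided rejection rate with no true difference = 1 − Φ(1.96 − d/SE) + Φ(−1.96 − d/SE).

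| d (SD) | d / SE | Two-sided rejection |
|---|---|---|
| 0.1 | 0.4 | 6.9% |
| 0.2 | 0.8 | 12.6% |
| 0.3 | 1.2 | 22.4% |

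With 40 per arm, SE = √(2/40) = 0.224 SD, and the movement is 0.45 to 1.34 SE.

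**5. Direction**

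Write the estimated effect as (month 12 difference) − (baseline difference), scored so that higher is better. Disappointment lowers the usual-care baseline. Reassurance, or a helpful first session, raises the STAND baseline. Each makes the baseline difference positive and pulls the estimate against STAND. At d = 0.2, the tail against STAND is 1 − Φ(1.16) = 12.3%. The tail in favour of STAND is Φ(−2.76) = 0.3%, down from 2.5%. The sign would reverse only if the first contact made STAND men report worse symptoms.

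**The case against.** The strongest reply is that this is a scheduling mismatch with limited reach. Much of that stands.

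- The primary test is a t-test on body fat measured by bioimpedance from C1D1. The PHQ-9 enters only the additional mixed model. Section 9.8.2 treats the secondary objectives as exploratory, with no multiplicity adjustment.
- The full shift passes through only in an unadjusted change score. Section 9.8.2 also plans repeated measures analysis of covariance. If baseline is its covariate, which is not stated, half of the shift passes through at correlation 0.5: 0.05, 0.10 and 0.15 SD against an SE of 0.25 × √(1 − 0.25) = 0.217 SD. The rejection rates become 5.6%, 7.5% and 10.7%.
- The endpoint is described as a mean percent change, whereas the illustration uses absolute change in SD units.
- A Day 1 form has one merit: it matches the timing of the body-fat and laboratory baselines.

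Four stronger readings are tempting, and the documents do not support them. A reader might infer that the 7.2 form is safely before allocation; but 7.2 and 7.3 share one window and do not order the forms before randomisation. A reader might take the rejection rates as a raised chance of falsely declaring STAND effective; under the natural mechanisms nearly all of the excess lies in the other direction. A reader might extend the point to every patient-reported endpoint; but patient satisfaction and patient insight (3.2.2) appear in neither list. A reader might expect sites to diverge; but 9.4 describes enrolment at one institution, so the risk is staff following different sections.

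None of this settles which form is the baseline.

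**Conclusion.** The point holds for the instruments listed in 7.2 and in footnote c to 7.1. The three sections cannot all be followed, and nothing in 8.2 or section 9 resolves them. Read as written, 7.1 puts the baseline after randomisation and possibly on the day of the first STAND session.

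The conflict and the order of events rest on the text alone. That men know their arm is inferred from the nature of the intervention and the absence of any described blinding; the documents do not call the trial open-label. The size is not known. The range of 0.4 to 1.2 SE depends on an assumed shift, an assumed correlation of 0.5 and unadjusted change scores, and should be read as sensitivity, not prediction. Its likeliest effect is to mask a quality-of-life benefit of STAND.

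The primary comparison of body fat is not affected. The 2D:4D analyses in 9.8.3, which use baseline empathy and percent change in quality of life, inherit the undefined baseline. In the non-randomised cohort the timing conflict applies but the allocation argument does not. This is a cheap improvement, not a threat to the trial's main conclusion.

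**What to change.** - **7.1, 7.2 and 7.4:** make them agree. For the randomised cohort, mark the questionnaire row in the screening column. If a Day 1 form is kept, list it in 7.4 as well.
- **7.2 and 7.3:** state that randomised men complete the questionnaires after consent and before randomisation. Moving the table mark alone is not enough, because randomisation shares the screening window. The paper and same-visit review rule for the PHQ-9 should be carried over to that visit.
- **Section 9:** state that this form is the baseline for the questionnaire endpoints and for the PHQ-9 covariate in 9.8.1. Treat any Day 1 form as a post-randomisation measurement.
- **Non-randomised cohort:** name one form completed before the first STAND session.
- **Cross-over men:** keep month 12 as the starting point, as 9.8.2 already does.

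The cost is a table correction, an ordering sentence and a few definitions. There is no added form, since 7.2 already schedules one at screening. The downside is that the questionnaire baseline may precede the Day 1 body-fat and laboratory baselines by up to 6 weeks. That gap arises in both randomised arms alike, so it does not favour either.

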4.1 Inclusion Criteria

- Histologic confirmation of adenocarcinoma of the prostate
- Receiving or planning to receive ADT with LHRH agonist or antagonist
- Expected duration of ADT at least 12 months from date of study consent
- Concurrent antiandrogen therapy allowed but not required
- First dose of LHRH agonist or antagonist no more than 6 months prior to date of study consent
- Prior/concurrent radiation allowed
- Other investigational agents in addition to LHRH agonist/antagonist are allowed (e.g. novel anti-androgens, androgen synthesis inhibitors)
- Prior androgen deprivation therapy allowed, provided there is documented evidence of testosterone recovery to > 150 ng/dL and greater than 12 months duration between last “effective” date of ADT and date of study consent
- **Randomized cohort only:**
 - No prior chemotherapy within 12 months of start date of study
 - No planned chemotherapy at least 12 months from study entry
- **Non-randomized pilot cohort:**
 - Concurrent chemotherapy (initiated within 3 months of study entry) or planned chemotherapy within 3 months of study entry
- ECOG performance status of 0 – 2
- Ability to sign written informed consent
- Willing to attend monthly clinic visits at UCSF

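### The baseline body-fat reading for the primary endpoint is specified on Day 1, after randomisation at screening, and no section defines baseline or requires the reading before allocation.

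*Combined protocol and SAP*

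**What the plan says.** - **Time of the reading.** The footnote to the 7.1 schedule gives "Percent body fat to be measured using bioimpedance device on C1D1, every 3 months, and end of month 12 on study". The Day 1 list in 7.4.1 includes "Height, weight, body mass index, and percent body fat by bioimpedance measurement".
- **Screening.** Section 7.2 lists only "Weight and body mass index". The combined 7.1 row, "Weight/Body Mass Index/Percent Body Fat", is ticked at Screening as well as Day 1 and carries the footnote above.
- **Randomisation.** In 7.1 it is ticked only in the Screening column. Section 7.3 states "Once eligibility is confirmed and patient has signed informed consent, patients will be stratified according to duration of ADT prior to study entry" and "Randomization must be completed within 6 weeks of day 1 of study". It does not ask for a body-fat reading first.
- **Masking and start of intervention.** No blinding of patient, staff or assessor is described, and only the STAND arm attends monthly. STAND counselling and modules are first ticked on Day 1, with no stated order relative to the bioimpedance reading.
- **Definition.** Sections 8.1, 9.5 and 9.8.1 refer to a baseline value without saying which visit supplies it.
- **Questionnaires.** Section 7.2 lists "Quality of life questionnaires (see Appendix 2") at screening, whereas the 7.1 table first ticks them on Day 1. Baseline PHQ-9 is a covariate in the mixed model of 9.8.1.

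**The concern.** Randomisation protects a comparison only for what is measured before allocation, or cannot be changed by knowing it. Here the denominator of the primary endpoint may be read after a man has been told his arm, in a trial of diet and exercise counselling.

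The bias could go either way. A man who expects the STAND clinic may start to change his habits. Any loss before Day 1 then lowers his baseline and is removed from the measured effect. A shift that raised the STAND baseline, or lowered the usual-care baseline, would exaggerate the effect instead. A t-test on percent change from baseline cannot separate either shift from a treatment effect.

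If both a screening and a Day 1 reading are taken, there is a second problem: no rule says which one enters the analysis.

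**Working it through.** **Order of events.** For a man followed as written in 7.2, 7.3, 7.4.1 and the footnote, the sequence is consent, eligibility, stratification and randomisation, then an interval of at most 6 weeks, then the first body-fat reading on Day 1. The Screening tick is the only contrary mark. The row combines three measurements, and BMI is needed at screening because 7.3 stratifies on it. The tick is therefore explained without a body-fat reading, although it does not exclude one.

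**The plan's own figures.** Section 9.2 assumes a mean increase of 12% (SD 17%) under usual care and 0% under STAND, with a two-sample t-test, two-sided 0.05, 80% power and 1:1 allocation.

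- Sample size: n = 2 × (1.960 + 0.842)² × 17²/12² = 31.5, so 32 per arm.
- Power at 32 per arm (noncentral t, 62 degrees of freedom, noncentrality d × √(32/2) = 4d): 79.8% for d = 0.71, and 79.4% for d = 12/17 = 0.706.
- Enrolment: 32/0.80 = 40 per arm.

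These agree with 9.2 and are not in dispute.

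**Illustration 1: dilution.** Assume STAND men lower body fat by a fraction s between allocation and Day 1, their month 12 value is unchanged, and SD stays at 17. The measured STAND change is 1/(1 − s) − 1.

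| s | Measured STAND change (%) | Difference (points) | Power |
|---|---|---|---|
| 0 | 0 | 12.0 | 79.4% |
| 1% | 1.01 | 10.99 | 72.1% |
| 2% | 2.04 | 9.96 | 63.6% |
| 3% | 3.09 | 8.91 | 54.1% |

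**Illustration 2: exaggeration.** Assume no true effect (both arms +12% at month 12) and a Day 1 value raised by s in one arm only. That arm's measured change is 1.12/(1 + s) − 1.

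| s | Measured change in that arm (%) | Spurious difference (points) | Two-sided rejection rate |
|---|---|---|---|
| 1% | 10.89 | 1.11 | 5.8% |
| 2% | 9.80 | 2.20 | 8.0% |
| 3% | 8.74 | 3.26 | 11.8% |

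**What the illustrations rest on.** The values of s are assumptions; the documents give none. Illustration 1 also depends on month 12 being fixed. If an early 2% loss persisted to month 12, the measured STAND change would be 0.98/0.98 − 1 = 0. The measured difference would stay at 12 points, against 12 − (−2) = 14 from a pre-randomisation baseline.

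**The case against.** - **Six weeks is a maximum.** Section 7.3 allows a much shorter gap, and no section says when men are told their arm. A reader might infer that every man knows his arm for six weeks before the reading; the text does not say so. That the trial is open-label is likewise an inference, though a safe one given a monthly clinic in one arm only.
- **No STAND contact is scheduled before Day 1.** The mechanism is anticipatory change, and a baseline at the start of the intervention is a recognised choice. This stands, and limits how large a shift is plausible. It is not a full answer. Section 7.5 has diet logs completed before dietitian visits, and Appendix 2 has a seven-day exercise record before trainer visits. If these apply to a first visit on Day 1, some STAND men begin self-monitoring before the reading.
- **The 7.1 row ticks Screening.** A pre-randomisation reading may therefore exist in practice. Its order relative to randomisation is still unstated, and nothing makes it the baseline.
- **Questionnaires.** A reader might infer that self-reported baselines follow allocation. The documents show only that 7.1 and 7.2 disagree.
- **ECOG.** The criterion "ECOG performance status of 0 – 2" is first ticked on Day 1, so a reader might infer that men are randomised before it is checked. Section 7.3 requires confirmed eligibility first, so this is a missing tick in the table and no part of the bias argument.

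**Conclusion.** The point holds as a gap in protection for the primary endpoint. As written, the baseline reading can be taken after allocation is known, and nothing in the plan prevents it or names another reading as baseline. The documents do not show that the baseline is biased, nor in which direction or by how much. A reader might take the power loss as a forecast, but the 1-3% shifts are assumed and month 12 is held fixed.

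Under those assumptions power falls from 79% to between 72% and 54%. Under the opposite assumptions the rejection rate with no true effect rises from 5% to between about 6% and 12%. With planned power of about 80% there is little margin, and the remedy is cheap, so the change should be made. The sample size need not change.

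**What to change.** 1. Take the bioimpedance reading at screening, before randomisation. The 7.1 row already ticks it; add it to 7.2 and to the footnote, and make it a condition of randomisation in 7.3.
2. In 9.5 and 9.8.1, define baseline body fat as the last value before randomisation. The Day 1 reading can remain as a later time point.
3. Reconcile 7.1 with 7.2 so that baseline questionnaires, including the PHQ-9 used as a covariate, are completed before randomisation.
4. Separately, as a minor table correction, tick ECOG at screening.

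**Cost.** Mostly wording, and at most one reading that the table already shows. The baseline would be up to 6 weeks older, with slightly more noise, equally in both arms. If a 12% yearly increase on ADT were linear, six weeks would account for 12 × 6/52 = 1.4%. Moving randomisation to Day 1 after the measurements would also work, but it is harder to run: STAND men see a rotating specialist that day, and the visit has to be booked.
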